#### 9.5.4.4 Expedited Reporting

The sponsor must inform investigators and regulatory authorities of reportable events, in compliance with applicable regulatory requirements, on an expedited basis (ie, within specific time frames). For this reason, it is imperative that sites provide complete SAE information in the manner described above.

#### 9.5.4.5      **Breaking the Blind**

Not applicable

#### 9.5.4.6      **Regulatory Reporting of Adverse Events**

Adverse events will be reported by the sponsor or a third party acting on behalf of the sponsor to regulatory authorities in compliance with local and regional law and established guidance. The format of these reports will be dictated by the local and regional requirements.

All studies that are conducted within any European country will comply with European Good Clinical Practice Directive 2005/28/EC and Clinical Trial Directive 2001/20/EC. All SUSARs will be reported, as required, to the competent authorities of all involved European member states.

#### 9.5.5      **Completion/Discontinuation of Subjects**

A subject (or subject's parent or guardian) may elect to discontinue study drug at any time for safety, medical, or personal reasons. Subjects who choose to discontinue study drug prior to PD will be followed in the post-study treatment follow-up period and continue to undergo regularly scheduled disease assessment until documentation of PD or start of an alternative anticancer treatment. All subjects who discontinue study drug will be followed for OS and all post progression cancer treatments administered will be recorded. Subjects may at any time withdraw consent for further study participation. No further data will be collected on subjects once consent has been withdrawn. All subjects who discontinue the study are to complete the study's early discontinuation procedures indicated in the Schedule of Assessments ([Table 5](#) and [Table 6](#)).

The investigator will promptly explain to the subject (or subject's parent or guardian) involved that the study will be discontinued for that subject and provide appropriate medical treatment and other necessary measures for the subject. A subject who has ceased to return for visits will be followed up by mail, phone, or other means to gather information such as the reason for failure to return, the status of treatment compliance, the presence or absence of AEs, and clinical courses of signs and symptoms.

Subjects who discontinue early from the study will be discontinued for 1 of these primary reasons: AE(s), lost to follow-up, subject choice, progression of disease, withdrawal of consent, pregnancy, study terminated by sponsor, or administrative/other. In addition to the primary reason, the subject may indicate 1 or more secondary reason(s) for discontinuation. Study disposition information will be collected on the Subject Disposition CRF.

#### 9.5.6      **Abuse or Diversion of Study Drug**

Not applicable.

### **9.5.7 Confirmation of Medical Care by Another Physician**

The investigator will instruct subjects to inform site personnel when they are planning to receive medical care by another physician. At each visit, the investigator will ask the subject whether he/she has received medical care by another physician since the last visit or is planning to do so in the future. When the subject is going to receive medical care by another physician, the investigator, with the consent of the subject, will inform the other physician that the subject is participating in the clinical study.

## **9.6 Data Quality Assurance**

This study will be organized, performed, and reported in compliance with the protocol, SOPs, working practice documents, and applicable regulations and guidelines. Site audits will be made periodically by the sponsor's or the CRO's qualified compliance auditing team, which is an independent function from the study team responsible for conduct of the study.

### **9.6.1 Data Collection**

Data required by the protocol will be collected on the CRFs and entered into a validated data management system that is compliant with all regulatory requirements. As defined by ICH guidelines, the CRF is a printed, optical, or electronic document designed to record all of the protocol-required information to be reported to the sponsor on each study subject.

Data collection on the CRF must follow the instructions described in the CRF Completion Guidelines. The investigator has ultimate responsibility for the collection and reporting of all clinical data entered on the CRF. The investigator or designee must sign the completed CRF to attest to its accuracy, authenticity, and completeness.

Completed, original CRFs are the sole property of Eisai and should not be made available in any form to third parties without written permission from Eisai, except for authorized representatives of Eisai or appropriate regulatory authorities.

### **9.6.2 Clinical Data Management**

All software applications used in the collection of data will be properly validated following standard computer system validation that is compliant with all regulatory requirements. All data, both CRF and external data (eg, laboratory data), will be entered into a clinical system.

## **9.7 Statistical Methods**

All statistical analyses will be performed by the sponsor or designee after the end of the Randomization Phase after database lock and randomization codes have been released. Statistical analyses will be performed using SAS software or other validated statistical software as required. Details of the statistical analyses will be included in a separate statistical analysis plan (SAP).

## 9.7.1 Statistical and Analytical Plans

The statistical analyses of study data are described in this section. Further details of the analytical plan will be provided in the SAP, which will be finalized before database lock.

### 9.7.1.1 Study Endpoints

Efficacy endpoints related to tumor assessments will be evaluated by independent imaging review (IIR) and investigator assessment.

#### 9.7.1.1.1 PRIMARY ENDPOINT

Progression-free survival (PFS) by IIR is defined as the time from the date of randomization to the date of the first documentation of PD or death (whichever occurs first) as determined by IIR using RECIST 1.1.

#### 9.7.1.1.2 SECONDARY ENDPOINTS

- Progression-free survival rate at 4 months (PFS-4m) by IIR is defined as the percentage of subjects who are alive and without PD at 4 months from the randomization date as determined by IIR of radiological imaging using RECIST 1.1. The PFS-4m rate is estimated using the Kaplan-Meier (K-M) method.
- Progression-free survival rate at 1 year (PFS-1y rate) by IIR is defined as the percentage of subjects who are alive and without PD at 1 year from the randomization date as determined by IIR of radiological imaging using RECIST 1.1. The PFS-1y rate is estimated using the K-M method.
- Overall survival (OS) is defined as the time from the date of randomization to the date of death from any cause. Subjects who are lost to follow-up and those who are alive at the date of data cutoff for the primary analysis, will be censored at the date the subject was last known to be alive, or date of data cutoff for the primary analysis, whichever occurs first. Overall survival rate at 1 year will be estimated using the K-M method.
- Objective response rate by IIR at 4 months (ORR-4m) is defined as the proportion of subjects who have best overall response of complete response (CR) or partial response (PR) as determined by IIR using RECIST 1.1 within the first 4 months.
- Objective response rate (ORR) by IIR is defined as the proportion of subjects who have best overall response of complete response (CR) or partial response (PR) as determined by IIR using RECIST 1.1.
- Safety will be assessed summarising the incidence of TEAEs and SAEs together with all other safety parameters.
- Assessment of population-based PK parameters of lenvatinib.
- Score changes from baseline for all PedsQL scales including Generic Core Scales and Cancer Module. Scores will be calculated for total generic score, total cancer score, each physical function subscale including physical health, psychosocial health, emotional function, social function, school/work function in the Generic Core Scales, and each subscales in the cancer module.

- Palatability and acceptability of the suspension formulation of lenvatinib in subjects receiving the suspension formulation in the study will be assessed using the Palatability Questionnaire (see [Appendix 4](#)).

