## 2 CLINICAL PROTOCOL SYNOPSIS

Compound No. E7080

Name of Active Ingredient: Lenvatinib

Study Protocol Title

A Multicenter, Open-label, Randomized Phase 2 Study to Compare the Efficacy and Safety of Lenvatinib in Combination with Ifosfamide and Etoposide versus Ifosfamide and Etoposide in Children, Adolescents and Young Adults with Relapsed or Refractory Osteosarcoma (OLIE)
	
Investigator	Principal Investigator: [name]
Sites	Approximately 80 sites worldwide
Study Period and Phase of Development	Approximately 36 months Phase 2
Objectives	
Primary Objective	To evaluate whether lenvatinib in combination with ifosfamide and etoposide (Arm A) is superior to ifosfamide and etoposide (Arm B) in improving progression-free survival (PFS) by independent imaging review (IIR) using Response Evaluation Criteria In Solid Tumors (RECIST 1.1), in children, adolescents, and young adults with relapsed or refractory osteosarcoma.
Secondary Objectives	The secondary objectives of the study are to:
	

1. Compare difference in PFS rate at 4 months (PFS-4m) between the 2 treatment arms per IIR

2. Compare difference in PFS rate at 1 year (PFS-1y) between the 2 treatment arms per IIR

3. Compare difference in overall survival (OS) and OS rate at 1 year (OS-1y) between the 2 treatment arms

4. Compare difference in objective response rate at 4 months (ORR-4m) between the 2 treatment arms per IIR

5. Compare difference in objective response rate (ORR) between the 2 treatment arms per IIR

6. Compare difference in safety and tolerability between the 2 treatment arms

7. Characterize the pharmacokinetics (PK) of lenvatinib, when administered in combination with ifosfamide and etoposide

8. Compare difference in health-related quality of life (HRQoL) as assessed by using the Pediatric Quality of Life Inventory (PedsQL) Generic Core Scales and Cancer Module between the 2 treatment arms

9. Assess the palatability and acceptability of the suspension formulation of lenvatinib in subjects receiving the suspension formulation in the study

Exploratory Objectives	The exploratory objectives of the study are to:

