## 9 INVESTIGATIONAL PLAN

### 9.1 Overall Study Design and Plan

This is a multicenter, randomized, open-label, parallel-group, Phase 2 study to compare the efficacy and safety of lenvatinib in combination with ifosfamide and etoposide versus ifosfamide and etoposide in children, adolescents, and young adults with relapsed or refractory osteosarcoma.

Approximately 72 eligible subjects will be randomized to 1 of the following 2 treatment arms in a 1:1 ratio within the strata:

- Arm A: lenvatinib 14 mg/m^2 (orally, once daily) plus ifosfamide 3000 mg/m^2/day (intravenously [IV], Day 1 to Day 3 of each cycle for a total of up to 5 cycles) and etoposide 100 mg/m^2/day (IV, Day 1 to Day 3 of each cycle for a total of up to 5 cycles)
- Arm B: ifosfamide 3000 mg/m^2/day (IV, Day 1 to Day 3 of each cycle for a total of up to 5 cycles) and etoposide 100 mg/m^2/day (IV, Day 1 to Day 3 of each cycle for a total of up to 5 cycles)

[figure not shown]
Randomization will follow a predefined randomization scheme based on the following stratification factors: time to first relapse/refractory disease (early [<18 months] or late [ $\geq$ 18 months]) and age (<18 and  $\geq$ 18 years).

The Sponsor will closely monitor enrollment, to ensure that a minimum of 36 subjects are <17 years of age at the time of informed consent.

The study will be conducted in 3 Phases: a Pre-randomization Phase, a Randomization Phase, and an Extension Phase.

The end of the study will be the date of data cutoff for the final analysis or the time of last subject last visit, whichever occurs later.

An overview of the overall study design is presented in [Figure 1](#).

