#### 9.1.2.2 Follow-Up Period

The Follow-up Period begins the day after the Off-Treatment Visit and will continue for up to 2 years after end of treatment for a subject, unless the subject withdraws consent or the sponsor terminates the study.

Subjects may at any time withdraw consent for further study participation. No further data will be collected on subjects once consent has been withdrawn, however, an investigator may consult public records to establish survival status if permitted by local regulations.

All adverse events (AEs), including serious adverse events (SAEs), will be captured for 30 days after the last dose of study drug.

All subjects who end study treatment without IIR confirmed PD, will continue to undergo tumor assessments every 6 weeks until Week 18, then every 9 weeks until Week 54, thereafter, every 12 weeks until IIR confirmation of radiographic evidence of PD as described in the tumor assessments in the assessment schedule, or until another anticancer therapy is initiated.

Subjects in both Arm A and Arm B will be followed for survival every 12 weeks ( $\pm 1$  week) and all subsequent anticancer treatments received will be recorded. Subjects who are being followed for survival at the time of data cutoff for the primary analysis (ie, at the end of the

Randomization Phase) will continue to be followed for survival during the Follow-up Period of the Extension Phase.

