#### 9.1.3.2 Follow-Up Period

The Follow-up Period will begin the day after the Off-Treatment Visit and will last for up to 2 years after end of treatment for a subject, unless the study is terminated by the sponsor, or the subject discontinues due to withdrawal of consent, or is lost to follow-up. Subjects will be treated by the investigator according to the prevailing local standard of care. Subjects will be followed every 12 weeks ( $\pm 1$  week) for survival and all subsequent anticancer treatments received will be recorded.

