### 9.3.3 Removal of Subjects From Therapy or Assessment

Subjects will continue to receive study treatment until any of the following occur:

- Progressive disease (as confirmed by IIR\*)
- Unacceptable toxicity
- Subject request
- Withdrawal of consent
- Termination of the study by the Sponsor

The investigator may discontinue treating a subject with study treatment or withdraw the subject from the study at any time for safety or administrative reasons. The subject may decide to discontinue study treatment or withdraw from the study at any time for any reason. The reason for discontinuation will be documented. If a subject discontinues study treatment, the subject will enter the Follow-Up Period and complete protocol-specified off-treatment visits, procedures, and survival follow-up unless the subject withdraws consent. The investigator should confirm whether a subject will withdraw from study treatment but agree to continue protocol-specified, off-treatment study visits, procedures, and survival follow-up, or whether the subject will withdraw consent. If a subject withdraws consent, the date will be documented in the source documents.

During the Follow-Up Period, subjects who have discontinued study treatment without progression should have disease assessments as per the appropriate tumor assessment schedule in [Table 5](#) and [Table 6](#) from the date of the last assessment until PD is documented or another anticancer therapy is initiated. After data cutoff for the primary analysis, tumor assessments may be performed as clinically indicated per institutional guidelines (but no less frequently than every 12 weeks), following the prevailing local standard of care, and IIR confirmation of radiographic evidence of PD will not be required.

All subjects will be followed for survival for up to 2 years after end of treatment for a subject, except where a subject withdraws consent or the sponsor chooses to halt survival follow-up after completion of the primary study analysis.

\*Confirmation of disease progression by IIR is only required during the Randomization Phase.

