#### 9.7.1.6      Efficacy Analyses

Efficacy analyses will be based primarily on the Full Analysis Set.

All primary statistical analyses will be conducted at the data cutoff date for the primary analysis (ie, when approximately 38 PFS events, as determined by IIR, are observed).

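### Overall survival is defined as censored at the PFS cutoff, although survival is followed beyond it and a later final analysis is named

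*Protocol*

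**What the plan says.** - **OS definition** (Protocol 9.7.1.1.2, repeated in the synopsis under Secondary Endpoints): subjects lost to follow-up or alive at the primary cutoff "will be censored at the date the subject was last known to be alive, or date of data cutoff for the primary analysis", whichever comes first.
- **Timing of analyses** (9.7.1.6): "All primary statistical analyses will be conducted at the data cutoff date for the primary analysis", which is reached at about 38 PFS events by independent review.
- **Follow-up after that cutoff** (9.1.2.2): subjects then in survival follow-up "will continue to be followed for survival during the Follow-up Period of the Extension Phase". Under 9.1.3.2 that period "will last for up to 2 years after end of treatment for a subject".
- **A later analysis** (9.1): "The end of the study will be the date of data cutoff for the final analysis or the time of last subject last visit", whichever is later. The synopsis and section 5.1 carry the same definition. The current efficacy sections do not describe the final analysis.
- **An exit** (9.3.3): survival follow-up need not continue where "the sponsor chooses to halt survival follow-up after completion of the primary study analysis".

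**The concern.** The censoring date is written into the endpoint itself and tied to a PFS event count. A subject alive at that date who dies a month later stays censored, whichever analysis is run. Yet children and young adults are to be contacted every 12 weeks after that date, and the study is said to end at a later cutoff.

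If the definition is applied as written, the later deaths cannot add to the survival comparison. If it is set aside when the final analysis is run, OS is reported under a rule that differs from the protocol's definition, and the change would be made after open-label data have accumulated. Either outcome can be avoided by settling the wording beforehand.

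**Working it through.** **1. The trigger.** With hazard ratio 0.4, one-sided alpha 0.025, power 80% and 1:1 allocation (9.7.2), the Schoenfeld formula gives 4 × (1.960 + 0.842)² / (ln 0.4)² = 31.4 / 0.840 = 37.4, rounded up to 38. The protocol's figure is reproduced.

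**2. When the trigger falls.** I took 36 subjects per arm, uniform accrual over 20 months, and exponential PFS with medians of 3.5 and 8.75 months.
- No dropout: 64.2 PFS events expected by month 32. If 40% of subjects never contribute an event, 0.6 × 64.2 = 38.5, which matches the protocol's month 32.
- If the 40% is instead exponential dropout reached by 32 or by 12 months, 38 events are expected at about month 18.5 or month 20.

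Month 32 is therefore the protocol's own case, and month 20 is the sensitivity case.

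**3. Inputs for deaths.** Arm A median OS is 16.3 months (the Study 207 combination result, section 7.3.1). The protocol gives no control-arm OS, so I assumed 8 to 16.3 months. Survival is exponential, with no loss to survival follow-up.

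**4. Formula.** With λ = ln 2 / median, expected deaths per arm at calendar month t ≥ 20 are 36 × [1 − (e^(−λ(t−20)) − e^(−λt)) / (20λ)].

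Example, Arm A at month 32: λ = 0.0425; e^(−0.510) = 0.600 and e^(−1.361) = 0.256; 0.344 / 0.850 = 0.404; 36 × 0.596 = 21.4.

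**5. Permitted follow-up.** As a simplification, each arm gets one limit: end of treatment plus 24 months.
- Arm B, five completed cycles: 105 days = 3.45 months, so 27.4 months.
- Arm A, treated to the assumed median PFS: 8.75 + 24 = 32.75 months.

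Deaths per arm are then 36 × (1 − e^(−λ × limit)). These limits serve the calculation only; they do not describe every subject.

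**6. Expected deaths, both arms:**

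| Arm B median OS (months) | Cutoff month 20 | Cutoff month 32 | Full permitted follow-up |
|---|---|---|---|
| 8 | 30.7 | 51.3 | 59.7 |
| 10 | 28.3 | 48.8 | 57.7 |
| 12 | 26.4 | 46.6 | 55.7 |
| 16.3 | 23.5 | 42.7 | 51.9 |

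**7. Share left out.**
- Month 32: (59.7 − 51.3) / 59.7 = 14% to (51.9 − 42.7) / 51.9 = 18%.
- Month 20: (59.7 − 30.7) / 59.7 = 49% to (51.9 − 23.5) / 51.9 = 55%.

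**8. Precision.** The SE of the log hazard ratio is about 2/√d, so CI width scales as 1/√d. On counts rounded to whole deaths:
- Month 32: √(43/52) = 0.909 and √(51/60) = 0.922, so the CI would be 9% and 8% narrower with full follow-up.
- Month 20: √(24/52) = 0.679 and √(31/60) = 0.719, so 32% and 28% narrower.

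Unrounded counts give 7 to 9% and 28 to 33%.

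**The case against.** **The protocol foresees a final analysis and refers analysis details to the SAP.** A reader might infer that the later deaths are discarded outright. The documents do not go that far: a later cutoff is named, and describing a further OS analysis is ordinary SAP content, so its absence here is not a fault. What remains is a conflict in what the protocol does state, because the only OS definition closes at the PFS cutoff whatever analysis follows.

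**The sponsor may stop survival follow-up after the primary analysis.** If it does, few later deaths are collected. That lowers the practical loss but leaves the passages to be reconciled.

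**OS is one of nine unranked secondary objectives, with no power claimed, and Arm B may cross over to lenvatinib.** Both points are fair. They limit what extra deaths can say about the randomised comparison and argue against overstating the matter.

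**Follow-up length by arm.** A reader might infer that follow-up counted from end of treatment gives Arm B a fixed, shorter window and so biases OS. As a general statement this is not supported. Arm B subjects who progress may receive lenvatinib until their next progression, and Table 7 gives them their own off-treatment visit and survival follow-up, so their window may also move with progression. While OS is censored at the primary cutoff, the limits in step 5 cost only 0.1 to 0.2 expected deaths by month 32. They allow at least 24 months in either arm, so the one-year OS rate is untouched. The clock matters only once later data are analysed.

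**Study period.** A reader might infer that the synopsis entry "Approximately 36 months Phase 2" is wrong, since 20 months of accrual, about 3 of chemotherapy and 24 of follow-up make about 47. But the figure is approximate, two years is a ceiling, and section 9.3.3 allows an earlier halt. It is not shown to be an error.

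**Conclusion.** The point holds as a contradiction between the OS definition and the follow-up and end-of-study text. Read literally, the definition keeps every death after the PFS cutoff out of OS in any later analysis.

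On the protocol's own timing the cost is modest: 14 to 18% of the expected deaths, and a CI that could be about 8 to 9% narrower. It becomes substantial, at about half the deaths and 28 to 32% of CI width, only if the 38 PFS events arrive near month 20. That depends on how the 40% dropout allowance operates.

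A reader might infer a gain of about 40%, from 22 deaths against 60: 1 − √(22/60) = 0.39. That requires a cutoff at month 17.8 with no dropout, before accrual ends, set against a month-47.5 count that ignores the two-year limit. The protocol's assumptions do not support it.

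The figures rest on exponential survival, uniform accrual, Study 207 OS for Arm A, an assumed control median, one follow-up limit per arm and no loss to survival follow-up.

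**What to change.** 1. In section 9.7.1.1.2 and the synopsis, define OS as censored at the last date known alive or the data cutoff of the analysis being performed, whichever is first.
2. In section 9.7.1.6, state that OS is re-analysed at the final-analysis cutoff with the same stratified log-rank test and stratified Cox model, and make this consistent with the sponsor's option in section 9.3.3 to halt survival follow-up.
3. For that later analysis, use a common calendar cutoff. State that permitted survival follow-up runs from each subject's end of treatment, which depends on progression in Arm A and in Arm B subjects who cross over, so late censoring may be related to prognosis.

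These are wording changes. They use survival contacts already planned every 12 weeks, and they should be settled before the primary cutoff because the trial is open-label. Following everyone to a fixed time after the last randomisation would go further: 24 months after the last subject means month 20 + 24 = 44, with added contacts for early Arm B subjects. That is a design change and is not needed to resolve this point.
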